Hypotheses: During saline/glycerol (control) infusions, patients with CPT2, VLCAD, and LCHAD/TFP deficiency will have similar ectopic lipid stores, and similar (or better) Rd and lower fasting Ra compared to control subjects and patients with MCAD deficiency. In contrast, during the intralipid infusion ectopic lipids will increase in the FAO patients and controls alike, but insulin sensitivity will worsen (decreased Rd) in controls and patients with MCAD deficiency, but not in those with CPT2, VLCAD, or LCHAD/TFP deficiency.

B. Specific Aim 2: To determine the effect of distinct FAO disorders on tissue-specific lipid metabolism and insulin resistance compared to matched controls. We will measure blood, skeletal muscle, and adipose levels of lipids, intermediates of FAO (including organic acids) and amino acids by metabolomics profiling, and adipose and muscle insulin signaling in FAO patients and matched controls participating in aim 1.

Hypotheses: In parallel with our hypothesized outcomes in Aim 1, we expect that CPT2, VLCAD, and LCHAD/TFP-deficient patients, despite intracellular accumulation of lipids and long-chain FAO intermediates in muscle and adipose tissue, will be “protected” from intralipid-induced insulin resistance by exhibiting greater insulin signaling pathway activation and glucose and FFA uptake than tissue from controls. On the other hand, accompanying the accumulation of medium chain FAO intermediates, subjects with MCAD deficiency will have reduced fat and muscle insulin action (similar to controls).

C. SIGNIFICANCE

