A. During fatty acid excess, long-chain acyl-CoAs and IMCL will accumulate, but decreased FAO will prevent an increase of redox equivalents and ROS generation resulting in normal insulin signaling and glucose uptake. **B.** With increased FAO upstream from MCAD, IMCL will still accumulate, but excess redox equivalents will lead to an oxidized mitochondrial environment with ROS generation, activation of serine kinases, inhibition of insulin signaling and decreased glucose uptake. IMCL=intramyocellular lipid. LCFAO = long-chain fatty acid oxidation. MCFAO = medium chain fatty acid oxidation. TCA = tricarboxylic acid cycle. ETC = electron transport chain. ROS= reactive oxygen species. PKC = protein kinase C.

[figure not shown]
infusion will increase IMCL in FAO patients and controls alike (**Figure 5A and B**). After the intralipid infusion, respiratory quotients will reflect FAO capacity and will be highest (indicating greater carbohydrate oxidation) in subjects with CPT2, VLCAD or LCHAD/TFP deficiency and lower (indicating greater fat oxidation) in MCAD-deficient subjects and controls. Based on our preliminary data of normal OGTTs in patients with inherited defects in the FAO defects, our findings of protection from high-fat-diet-induced insulin resistance in VLCAD $-\text{}/-$ mice, as well as studies that have shown that blocking FFA entry into mitochondria can alleviate high-fat-diet-induced insulin resistance in animal models,(56, 57) we anticipate that subjects with defects in CPT2, VLCAD, and LCHAD/TFP enzymes will be protected from high-fat-diet-induced insulin resistance, essentially "blocking" long-chain FA oxidation (flux) at a level that avoids accumulation of metabolic intermediates that adversely affect insulin signaling (**Figure 5A**). On the other hand, we anticipate that increased oxidative flux of fatty acids from long-chain fatty acids to medium chain metabolites will not provide the same protection from excess fatty acid substrate, impairing insulin signaling in patients with MCAD deficiency (**Figure 5B**) who will exhibit insulin resistance (compared to control infusion days) in muscle (reduced glucose disappearance, reduced insulin signaling ex-vivo), and adipose tissue (reduced suppression of FFA during the clamp) similar to controls. We predict that the degree of FFA-induced insulin resistance in these subjects will be similar to control subjects (**Figure 5B**).

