The following day, the clamp study will begin at approximately 6:00 AM and end at about 4:00 PM (Day 2; **Figure 11**). Indirect calorimetry to measure energy expenditure and respiratory quotient for estimation of fat oxidation will be performed in the last hour of the clamp. The order of the intralipid vs. glycerol/saline infusion during HEC will be randomly assigned. Subjects will rest overnight and consume a standardized breakfast the following day (Day 3) and be discharged to home. Subjects will return 4 months later and repeat the admission with the alternative clamp procedure. If accurate clamp results are not achieved at Visit 1 or 2, the subject may be asked to return for another study visit to repeat the clamp procedure, DEXA, indirect calorimetry and/or biopsies. During periods of hospital recommendations for decreased in-person contact, study visits will be postponed until study staff are notified of return to normal research visit operations.

¹H and ¹³C MRS Procedure: of the liver and muscle: will be performed as previously described(18, 30) prior to (-100 min) and following both clamp procedures. Each subject will complete 4 MRS measurements of liver and muscle lipid content (**Figure 11**). Image-guided, ¹H localized, MRS following high-resolution T-weighted spin-echo imaging will be performed on a Siemens 3T whole-body system. Radiofrequency surface coils will be used for region-of-interest (ROI) voxel localization and spectroscopy data acquisition. Depending on the schedule for the MRS instruments and to allow for more time for a meal before the testing, the MRS measurements may not be completed until approximately 5:30 PM.

MRI of the abdomen to quantify visceral and subcutaneous fat: Although not a primary outcome, these measures will be acquired using a Siemens 3T system as previously described (18, 30).

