The primary analyses to compare disease groups with healthy controls will use mixed models with a random effect for matched pair to allow for correlation between the observations on the matched observations. In addition to the random pair effect, a disease effect (disease versus healthy), and a diagnostic group effect (CPT2, VLCAD, LCHAD/TFP, MCAD), we will also incorporate a fixed effect for the order of testing (interlipid infusion tested first or second). The hypotheses focus on the comparisons between diseased individuals and their matched controls with regard to the difference in outcomes under the two conditions (glycerol vs interlipid infusion). For these analyses, we will use the difference in a given outcome (e.g., Rd uptake) between infusion conditions as the dependent variable and compare these differences between diseased and matched controls, separately for the four diagnostic groups (CPT2, VLCAD, LCHAD/TFP, MCAD). Although we will conduct a formal test of interaction of disease (disease vs healthy) and diagnostic group, we are not powered for such a test and, hence, will focus on separate inferences for the four disease groups. Note that, as indicated in the hypotheses, we expect to find differences between the controls and the CPT2, VLCAD, and LCHAD/TFP subjects, but not between the controls and the MCAD subjects. For the latter comparison, our emphasis will be on estimating the magnitude of the mean differences via 95% confidence intervals rather than formal hypothesis testing. We will use a significance level of 0.05 for each outcome comparison, with no adjustment for multiple comparisons due to the limited sample sizes. We are unable to increase sample sizes due to the small study populations and budgetary constraints, so cannot power the study to take into account the multiple comparisons. However, we will present for each outcome, both unadjusted p-values as well as p-values adjusted for the two multiple comparisons (one for each disease group) using the Holm procedure.(38)

Power Considerations:

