For each outcome, we have two measurements on every subject, one for each infusion condition. Our analyses will focus on comparisons between patients and controls of the *differences between outcomes* under the two conditions. We expect to see meaningful differences between controls CPT2, LCHAD/TFP, and VLCAD-deficient participants. These are the groups of interest for power calculations, whereas for MCAD, our aim is to provide useful descriptive information. There are two sets of correlations

between measures that need to be considered in power calculations (and statistical analyses). The first is the correlation between outcome measures on a given subject under the two infusion conditions, the second is the correlation of the differences in outcomes under the two infusion conditions, between each subject and his/her matched pair. For power calculations, we considered various values for each of these two correlations and used standard deviation estimates for each infusion condition as reported for glucose infusion rate (GIR) and for PDK4 mRNA levels (81, 94). GIR is a primary result during the HEC, closely related to insulin resistance (specific aim 1). PDK4 message is associated with our hypothesized mechanisms for insulin resistance in muscle and adipose tissue (Specific Aim 2). Mean and SD values for these outcomes in healthy controls are given in **Table 5**. We assume that normal controls and MCAD subjects will have mean outcomes as given in the table but that subjects with CPT2, VLCAD, and LCHAD/TFP disorder will have mean decreases when given the interlipid infusion that are less than 10% from that under the glycerol infusion condition for GIR and a mean increase of less than 100% for PDK4 mRNA. That is, we expect the mean change from glycerol infusion condition to be less than 5.7, and 0.18 for GIR, and PDK4 mRNA, respectively, for the CPT2, VLCAD, and LCHAD/TFP subjects.

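### Four liver and muscle MRS scans per subject, but the analysis takes one value per infusion and gives the pre-clamp scans no role; prespecify a pre-clamp-adjusted post-clamp difference in the joint model

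*Combined protocol and SAP*

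**What the plan says.** The MRS paragraph in section III (Study Design) places scans "prior to (-100 min) and following both clamp procedures" and adds: "Each subject will complete 4 MRS measurements of liver and muscle lipid content". Ectopic fat is a named outcome of Specific Aim 1.

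Section V (Statistical Analysis) describes a mixed model: "we will use the difference in a given outcome (e.g., Rd uptake) between infusion conditions as the dependent variable and compare these differences". Its terms are a random matched-pair effect and fixed effects for disease, diagnostic group and order of infusion. There is no pre-clamp term. Power Considerations adds: "For each outcome, we have two measurements on every subject, one for each infusion condition".

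The Aim 1 hypotheses speak of a level on the control day ("During saline/glycerol (control) infusions, patients with CPT2, VLCAD, and LCHAD/TFP deficiency will have similar ectopic lipid stores") and a rise on the lipid day ("during the intralipid infusion ectopic lipids will increase in the FAO patients and controls alike"). Anticipated Results repeats the rise: "infusion will increase IMCL in FAO patients and controls alike". The Figure 11 legend and the rationale for the clamp approach also use the language of accumulation and re-measurement.

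Study Design lets a subject return to "repeat the clamp procedure, DEXA, indirect calorimetry and/or biopsies" if a clamp fails. MRS is not in that list.

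**The concern.** With four scans, at least three analyses fit the wording: compare the post-clamp scans, compare the pre-to-post changes, or compare the post-clamp scans adjusted for the pre-clamp ones. Which is most precise depends on correlations and SDs that the documents do not give for MRS, so the choice could be made after the data are seen. Recruitment is fixed at 8 patients per diagnostic group, and the plan says the sample cannot be increased. The pre-clamp scans are already scheduled, so leaving them without a role may waste precision.

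**Working it through.** **The plan's own figures.** No power or precision is stated for any MRS outcome. The stated figures concern glucose infusion rate (GIR) and PDK4 with n = 10. I used a two-sided paired t-test, with within-subject SD √(s₁² + s₂² − 2ρ₁s₁s₂) multiplied by √(2(1 − ρ₂)) for the pair contrast.
- GIR, zero correlation: √(9.3² + 7.8²) = 12.14; × √2 = 17.17; difference 31.5 − 5.7 = 25.8; power 98.8% (stated: about 97%).
- PDK4, difference 0.62 − 0.18 = 0.44: 62.6% at zero correlation and 78.1% at 0.25/0.25 (stated: 63% and 78%).

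The pair-level framework therefore matches the plan's, and I carried it over to MRS.

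**MRS set-up.** For each patient-control pair, let y be the patient's intralipid-minus-glycerol difference in post-clamp lipid minus the control's, and x the same quantity from the pre-clamp scans. Scale y to SD 1. Two inputs are **assumed**, because the documents do not give them: r = corr(x, y), from 0 to 0.8, and k = SD(x)/SD(y), from 0.17 to 1.1. To show how widely k might vary, I let the pre-clamp SD equal the glycerol-day SD in Table 5. GIR then gives k ≈ 1.08 and PDK4 gives 0.17 to 0.22. These are not MRS data. The effect used for power, 0.8 SD, is also assumed.

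**Joint fit, four groups × 8 pairs, one slope:**
- Post-clamp only: noncentrality 0.8 × √8 = 2.26 on 28 df.
- Change score: the same, divided by √(1 + k² − 2kr).
- Adjusted: variance (1 − r²)(1/8 + x̄²/Sxx) on 27 df, averaged over x̄²/Sxx. On average this inflates 1/8 by 1 + 1/26.

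Power at 0.8 SD:

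| r | 0 | 0.2 | 0.3 | 0.5 | 0.7 | 0.8 |
|---|---|---|---|---|---|---|
| Post-clamp only | 59% | 59% | 59% | 59% | 59% | 59% |
| Adjusted (any k) | 57% | 59% | 61% | 70% | 85% | 95% |
| Change, k = 1 | 34% | 41% | 45% | 59% | 80% | 93% |
| Change, k = 0.5 | 50% | 57% | 61% | 71% | 84% | 90% |
| Change, k = 0.2 | 57% | 61% | 63% | 66% | 71% | 73% |

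Expected 95% CI half-width, in SDs of y:

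| r | 0 | 0.3 | 0.5 | 0.7 |
|---|---|---|---|---|
| Post-clamp only | 0.72 | 0.72 | 0.72 | 0.72 |
| Adjusted | 0.73 | 0.70 | 0.63 | 0.52 |
| Change, k = 1 | 1.01 | 0.85 | 0.72 | 0.56 |
| Change, k = 0.5 | 0.80 | 0.70 | 0.62 | 0.53 |

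The worst shortfall against the best of the three, over the assumed range, is 1.7 power points for adjusted, 36 for post-clamp only and 28 for change. Fitting order as well costs every method 1 to 2 points (post-clamp only 57%; adjusted 56% at r = 0 and 68% at r = 0.5).

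**Separate 8-pair fits.** Post-clamp only has 50% power. Adjusted has 43% at r = 0, 46% at r = 0.3, 53% at r = 0.5 and 69% at r = 0.7, breaking even near r = 0.42. Its worst shortfall is about 8.6 points. For r up to 0.3 the worst shortfall is 7.4 points, against 3.7 for post-clamp only.

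**Wrong common slope.** With true slopes of 0.2, 0.4, 0.6 and 0.8 in the four groups, simulation shows no material bias. Per-group type I error is 4.5% to 5.6% if residual SDs are equal. If total SDs are equal instead, so that residual SDs differ, it runs from 1.5% to 9.4%.

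**The case against.** The strongest reply is that the text leans towards the pre-to-post change, and that one change per infusion fits the two-measurement sentence in Power Considerations. One clarifying sentence would then be enough, and choosing adjustment over change is a preference. Part of this stands. A reader might infer that four scans contradict the two-measurement sentence; they do not, because either reading reduces to one value per infusion. But the lean is not a definition, and the control-day hypothesis is about a level.

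A second reply also stands in part. Section V emphasises separate inferences for the four groups, and in separate 8-pair fits adjustment can lose about 9 points. However, the section describes a model with disease and diagnostic-group effects and a test of their interaction. A joint fit with group-specific contrasts is consistent with that, and the recommendation depends on it.

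Third, the expected MRS result is a rise in all groups, so power for a 0.8 SD group difference is not the planned question. I accept this: interval width is the relevant measure, and power only ranks the options.

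Fourth, the groups have different enzyme defects, so a common slope and variance may fail. This also stands. A slope check with 8 pairs per group has little power, so fits that relax these assumptions should be reported regardless of any test.

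**Conclusion.** The gap is real, and closing it is a cheap gain in precision. Adjustment in the joint model is at most about 2 power points below the best alternative for r from 0 to 0.8 and k from 0.17 to 1.1. At r = 0.5 it narrows the interval from 0.72 to 0.63 SD; at r of 0.3 or less it changes little in either direction. All of this is conditional on assumed r and k.

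Three stronger readings are not supported. A reader might infer that ignoring the pre-clamp scans biases the comparison. Infusion order is randomised and the pre-clamp scan precedes the infusion, so, apart from order or carry-over effects, all three analyses estimate the same contrast. A reader might infer that adjustment is always best. It is not: the change score can tie it or beat it by 1 to 2 points in the joint fit, and by about 9 in separate fits. Finally, a narrower interval does not by itself show that patients and controls respond similarly.

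**What to change.** In section V, for intrahepatic and intramyocellular lipid:

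1. Name the between-infusion difference in the post-clamp value as the outcome, with the between-infusion difference in the same-visit pre-clamp value as a covariate.
2. Fit this in the single joint model over all four diagnostic groups, with a common slope, group-specific patient-control contrasts, and the pair and order terms. Do not use separate 8-pair fits.
3. Report two sensitivity analyses: the pre-to-post change, and a fit with group-specific slopes or variances.
4. Say in Power Considerations that MRS has four scans per subject, reduced to one adjusted difference.
5. State which scans are used when a clamp is repeated, and how a missing pre-clamp scan is handled. Setting the covariate to its overall mean keeps the pair. With 10% of pairs affected, simulated power is 61% at r = 0.3 and 68% at r = 0.5, against 56% and 64% if those pairs are dropped.

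If the authors prefer the change as the main analysis, they should say so before the data are seen and keep the adjusted model as a sensitivity analysis.

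The cost is wording, since every scan is already planned. The statistical price is one degree of freedom, 1 to 2 power points if r is near zero, and the reliance on a common slope and residual variance that the second sensitivity analysis is meant to expose.

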To address these controversies, we will study a unique population of patients with inherited defects in one of four mitochondrial enzymes in the FAO pathway: 1) carnitine palmitoyltransferase 2 (CPT2); 2) very long-chain acyl-CoA dehydrogenase (VLCAD); 3) trifunctional protein (TFP, which includes long-chain 3-hydroxyacyl-CoA dehydrogenase (LCHAD)); and 4) medium-chain acyl-CoA dehydrogenase (MCAD). These proteins are required for the oxidation of sequentially shorter fatty acids (long-chain and medium-chain), respectively. We will use these patients to formally test the hypothesis that *intrinsic defects in mitochondrial function involving oxidation of long-chain, but not medium-chain, fatty acids are sufficient to prevent intralipid-induced insulin resistance.*

In a randomized, crossover study design, patients and a healthy control group will receive infusions of either intralipids or a control solution during hyperinsulinemic-euglycemic clamps. Glucose appearance (primarily due to hepatic glucose production) and glucose disposal (primarily by muscle tissue) will be measured, as will intrahepatic and intramyocellular lipid content (ectopic fat) by magnetic resonance spectroscopy, metabolite accumulation in muscle and fat using advanced metabolomics methodology, and insulin signaling pathway component expression and activation in the same biopsy samples.

In the first studies to test the relationships between impaired FAO, accumulation of intracellular lipid and lipid oxidation intermediates, and insulin resistance in humans, we propose the following specific aims:

A. Specific Aim 1: To measure the effect of intralipid infusions on ectopic fat and systemic glucose metabolism in FAO patients and matched controls. We will measure ectopic lipid deposition in muscle and liver by ¹H magnetic resonance spectroscopy (MRS) as well as glucose appearance (Ra) in the fasting state and insulin-mediated glucose disposal (Rd) during hyperinsulinemic-euglycemic clamps and co-infusion of either intralipids or saline/glycerol in patients with a FAO disorder and matched controls.

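### The long-chain-but-not-medium-chain hypothesis has no contrast aimed at it, and the statement that the interaction test lacks power has no calculation and is not borne out for GIR

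*Combined protocol and SAP*

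**What the plan says.** The opening statement of the protocol reads "We will use these patients to formally test the hypothesis that" defects in "oxidation of long-chain, but not medium-chain, fatty acids are sufficient to prevent intralipid-induced insulin resistance". The hypotheses under Specific Aim 1 repeat this for glucose disposal: "insulin sensitivity will worsen (decreased Rd) in controls and patients with MCAD deficiency, but not in those with CPT2, VLCAD, or LCHAD/TFP deficiency". Both say that long-chain and MCAD patients respond differently.

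Section V (Statistical Analysis) frames the inference another way: "The hypotheses focus on the comparisons between diseased individuals and their matched controls". The between-infusion difference is compared between patients and controls separately in CPT2, VLCAD, LCHAD/TFP and MCAD. Differences are expected in the three long-chain groups "but not between the controls and the MCAD subjects", and the MCAD comparison is to be read mainly from a 95% confidence interval. A formal test of disease by diagnostic group will be run, but "we are not powered for such a test and, hence, will focus on separate inferences for the four disease groups".

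Under Power Considerations the long-chain groups are the ones of interest, "whereas for MCAD, our aim is to provide useful descriptive information". Tables 5 and 6 and the surrounding text give power only for long-chain patients against controls. The end of Section III says that Aim 2 changes will be compared between long-chain patients, MCAD patients and controls, but names no model, contrast or test.

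**The concern.** A significant patient-versus-control difference in one disorder, set beside an interval that includes zero in another, does not show that the two disorders differ. With 8 pairs per group the MCAD result could miss a real difference by chance alone, and the picture would then look like the hypothesis.

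The only between-disorder test with a stated form is the interaction. With four diagnoses it has 3 df. It can reject because the long-chain disorders differ among themselves, and it spreads its power over patterns the hypothesis does not mention. The plan sets it aside on grounds of power without a figure. If that reason does not hold for a main clamp outcome, the plan has moved its emphasis away from the question it promised to answer, with no calculation to justify the move.

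**Working it through.** **Inputs.** Section II: 8 patients per diagnosis, each with a matched control. Table 5: GIR SDs 9.3 (glycerol) and 7.8 (intralipid); mean change 31.5 in controls and MCAD against 5.7 in long-chain patients, a difference of 25.8. PDK4 SDs 0.06 and 0.38; difference 0.62 − 0.18 = 0.44. Power Considerations: "We assume that normal controls and MCAD subjects will have mean outcomes as given in the table", so the MCAD-minus-control difference is 0. Level 0.05, taken as two-sided. My assumptions: the healthy-volunteer SDs apply to patients, variance is common across groups, and all pairs are complete. Ranges run from zero correlation (0/0) to 0.25 within subject and 0.25 between pair members (0.25/0.25), unless stated.

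**SD of the pair difference in change** = √[2(s1² + s2² − 2·r1·s1·s2)(1 − r2)].
- GIR at 0/0: √[2(86.49 + 60.84)] = 17.17. At 0.25/0.25: √[2 × 111.06 × 0.75] = 12.91.
- PDK4: 0.544 at 0/0, 0.453 at 0.25/0.25, 0.354 at 0.50/0.50.

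**Reproducing the plan's figures** (paired t, n=10). PDK4 gives 62.6% and 78.1%, against the printed 63% and 78%. GIR at zero correlation gives 98.8%, against about 97%. An SD of 18.81 (9.6% larger) would give 97% at n=10, as would roughly n=9 with the Table 5 SDs (97.5%). The documents do not settle which, so the GIR results are also shown with the larger SD.

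**3-df interaction, 8 pairs per group.** GIR group differences are (25.8, 25.8, 25.8, 0), mean 19.35. At 0/0, λ = 8 × (3 × 6.45² + 19.35²)/17.17² = 13.55. Noncentral F with 3 and 28 df gives 83%. At 0.25/0.25, λ = 23.97 and power is 98%.

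**1-df contrast** (mean of the three long-chain differences minus the MCAD difference). At 0/0, SE = 17.17 × √(1/24 + 1/8) = 7.01; 25.8/7.01 = 3.68; noncentral t with 28 df gives 94%. At 0.25/0.25, SE = 5.27 and power is 99.7%.

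**Separate test in one long-chain group.** On its own 7 df: 95% to 99.8%. On the same pooled 28 df as the contrast: 98% at zero correlation.

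**Sensitivity for GIR** (the variations are my assumptions):

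| Case | 3-df | 1-df |
|---|---|---|
| SD 9.6% larger | 75–95% | 90–99% |
| Difference 20 | 60–86% | 79–96% |
| SD 25% larger | 63–88% | 81–97% |
| Both of the last two | 40–66% | 60–83% |
| 6 pairs per group | 68–91% | 86–98% |
| MCAD half protected | 27–46% | 43–66% |
| One long-chain group unprotected | 93–99.7% | 66–88% |

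**PDK4.** 3-df: 31%, 44% and 66% at 0/0, 0.25/0.25 and 0.50/0.50. 1-df: 48%, 63% and 84%. **Rd:** no SD is given, so power cannot be computed.

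**What separate inferences can show when the disorders do not differ.** Let all four groups share one true GIR difference d, and let p be the power of a single 8-pair test at d. The chance that at least two long-chain groups are significant while the MCAD interval includes zero is [3p²(1 − p) + p³](1 − p). For all three it is p³(1 − p). At half protection, d = 12.9:
- 0/0: p = 0.450, giving 23% and 5%.
- 0.25/0.25: p = 0.680, giving 24% and 10%.

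The two-of-three rate is lower at small or full effects: 5–9% at d = 6, and 5% down to 0.2% at d = 25.8. The 1-df contrast rejects in 5% throughout, because its null hypothesis is true.

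**The case against.** The strongest reply is that the plan is cautious and already guards against the misreading. It commits to the interaction test, reports MCAD as an interval and calls it descriptive. Its remark on power covers all outcomes, and for PDK4 it is right. Most of this stands as a limit on the point. A reader might go further in four ways that the documents do not support.

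- **That long-chain is never compared with MCAD.** The interaction test does so in omnibus form, and the end of Section III announces a comparison. What is missing is a contrast aimed at the hypothesis.
- **That power gives no reason to prefer the separate tests.** On equal pooled 28 df at zero correlation, the separate test has 98% against 94% for the contrast. With SD 25% larger it is 91% against 81%; with a difference of 20 as well, 72% against 60%. The separate tests also do not depend on where MCAD lies. They have a real advantage, but under the plan's own GIR inputs it is modest.
- **That the MCAD interval cannot exclude half protection.** Its expected half-width on 7 df is 14.4 at zero correlation and 10.8 at 0.25/0.25. If MCAD equals controls, it excludes 12.9 in 45% to 68% of trials.
- **That a misleading pattern will occur in a quarter of trials.** The 23–24% needs a two-of-three reading and an effect near the worst case. The plan states no rule for what supports the hypothesis; requiring all three groups gives 5–10%.

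It is also fair to say that the contrast alone does not settle the hypothesis. A claim that a defect is sufficient to prevent resistance needs evidence against controls too, and the contrast could reject because MCAD is worse than controls.

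**Conclusion.** The point holds as a gap in the analysis plan. A differential hypothesis is promised a formal test, the emphasis falls on four separate 8-pair comparisons, and the one between-disorder test is a general 3-df interaction set aside without a calculation.

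For GIR, under Table 5 inputs with MCAD equal to controls and no dropout, that reason is not supported: 83–98% for the 3-df test and 94–99.7% for a targeted contrast. These figures rest on a large assumed difference and on SDs from healthy volunteers. The contrast drops to 43–66% if MCAD is half protected. The reason is fair for the PDK4 3-df test (31–66%) and cannot be checked for Rd, the outcome named in the Aim 1 hypothesis. A reader should therefore not conclude that the trial is well powered for the differential question across its outcomes. Even where power is low, though, the contrast and its interval estimate the quantity the hypothesis is about, which the separate comparisons do not.

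**What to change.** In the model on all 32 pairs that includes the disease-by-diagnosis term, prespecify one 1-df contrast with its 95% CI: the equal-weight mean of the CPT2, VLCAD and LCHAD/TFP patient-minus-control differences, minus the MCAD patient-minus-control difference. State that it is interpreted together with the long-chain-versus-control contrasts. Keep the 3-df test, the four group contrasts and the MCAD interval. Replace the general statement on power with power by outcome and the assumptions used: adequate for GIR under Table 5 but sensitive to effect size, SD, dropout and partial MCAD protection; low for the PDK4 3-df test; not computable for Rd until an SD is stated.

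The cost is wording only, with no new patients or data. The downside is that the contrast averages over three disorders. If one is unprotected it has less power than the 3-df test (66% against 93% for GIR at zero correlation). The Innovation section also wants to locate the level of the defect, which the average cannot do. Both are reasons to add the contrast to the planned analyses and not to substitute it for them.
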